6.5 Randomization

Randomization will occur during the contact call immediately after patients have been told of their smoking treatment options. The TCOS will then use randomization tables developed by UW-CTRI to randomize potential enrollees, blocked by clinic, sex, and race, into 1 of 3 engagement incentive conditions (\$0, \$100, or \$50). After randomization, patients will be offered smoking treatment with the incentive for treatment entry (engagement) to which they had been randomized. This offer will require the participant to agree to set a stop-smoking quit date within the next 30 days. This offer will occur prior to the patient's provision of consent to participate in research. The patient must be offered the incentive up-front to see if this increases their treatment engagement (which necessarily includes agreement to it/consent); offering the incentive after agreeing to participate in treatment would not reveal the effects of the incentive on spurring engagement. Thus, we are interested in the effects of incentives on both agreement to enter treatment and actual likelihood of engaging in it. If a patient decides to accept the treatment offer, s/he will be consented and will set a target quit date with the TCOS (within 1 month of the contact phone call). For patients who are unwilling to set a stop-smoking quit date within the next 30 days the TCOS will describe all stop-smoking treatment options that are available as part of usual care and encourage the patient to call the TCOS back when ready to set a quit date within 30 days. For patients who decline the research study, the TCOS will describe all stop-smoking treatment options that are available as part of usual care and provide quit smoking treatment as usual.

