4.2 Aims

Primary Aim

1. To determine the relations between treatment engagement financial incentive amounts offered and likelihood of patient engagement in smoking cessation treatment.
 - a. Primary outcome measure: Patient engagement in smoking cessation treatment (defined as setting a TQD and completing the two phone counseling calls).

Exploratory Aims

1. To determine the incremental cost-effectiveness of the different financial engagement incentive amounts with regard to total program costs vs. usual care, net monetary benefit (NMB), cost per quit, and incremental cost-effectiveness ratios (ICERs), with the last determined with regard to cost of additional smoker recruited and each additional individual who quits smoking.
2. To determine the representativeness of smoking treatment reach and smoking abstinence outcomes generated by the various engagement incentive amounts with regard to different groups of smokers: e.g., those low in socio-economic status, priority populations, different racial and ethnic groups.
3. Conduct exploratory analyses on the effects of the different incentive engagement amounts on biochemically confirmed point-prevalence 6-month abstinence, and determine whether incentive condition affects abstinence via effects on smoking treatment engagement (i.e., whether smoking treatment engagement mediates the relations between different engagement incentive conditions and 6-month smoking abstinence).

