6.4 Consent & Enrollment

GHC-SCW TCOS staff will be responsible for program implementation and data documentation (using existing EHR and administrative data fields) except for 3- and 6-month Follow Up survey collection completed by the research staff. Only limited patient and systems data will be shared with the research team documenting which patients were called as standard practice but declined study participation.

All patients who agree to the study offer – tailored to their assigned Treatment Engagement Incentive value (Attachment B: Invite script), and pass the inclusion and exclusion criteria for Treatment Engagement Incentive study participation will be read an oral consent script by a healthcare system TCOS (see uploaded Recruitment Call script). The consent script read to participants over the phone conveys the key points regarding study procedures; risks; and participant rights, protections, and benefits, and does so in accessible language (assessed for reading level). The consent will inform patients that some monetary payments may be offered as part of the study for engaging in study components, including \$20 for completing a telephone survey 6 months after their original Target Quit Date and \$50 for those who report smoking abstinence at 6 months who complete an in-person breath CO breath test, urine, or saliva test, but the [incentive] amounts available will not be disclosed (so that some patients will not refuse further engagement due to disappointment with their incentive amount). Prospective participants will be given an opportunity to ask questions and raise concerns during this process, which will be addressed prior to seeking oral consent. Informed consent for study participation will be formally documented electronically in the UW-ICTR REDCap instance study database. Following enrollment for those who consent, TCOS staff will send out a letter in hard copy to the participant at the address provided (see uploaded Study Information Sheet). This letter will remind the participant of study procedures and will include a detailed study information enclosure containing all required elements of informed consent and HIPAA authorization.

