7.0 Study Treatments and Experimental Conditions

Smoking cessation treatments will not be experimentally manipulated or varied as a function of research participation. Participants and non-participants will be treated per standard clinical protocols for tobacco use. The experimental conditions (i.e., the incentives) in the study are intended to effect smoker *engagement* in treatment as offered by healthcare system personnel. The primary differences between research study participation and usual care with regard to smoking treatment are: 1) the consent process, 2) randomization to treatment engagement incentive condition and provision of such incentive, 3) follow-up to determine patient smoking status. Importantly, actual smoking cessation treatments (counseling and medications, the existing GHC-SCW standard of care) will be identical for both those who chose to participate in the study and those who do not (Figure 2).

7.1 Incentives In 2 of our recent studies^{4,5}, incentive-driven increases in counseling use mediated incentive effects on abstinence in Medicaid-insured smokers. Given the significant savings associated with smoking cessation⁸, modest incentives to engage in treatment may well be cost-effective if they increase quitting. Modest incentives (\$25 or \$50) also improve attendance at primary care visits⁹. Thus, evidence supports modest, utilization-contingent incentives for use of both smoking cessation and primary care treatment. The proposed project

will evaluate the effects of incentives of varying magnitude for smoking treatment engagement (rather than achieving abstinence) in primary care.

To identify an especially effective incentive amount, three different incentive value conditions will be evaluated (0, \$100, and \$50). The incentive will be tied to readily observable *initiation* of treatment (i.e., setting a target quit date within 30 days on a call with a TCOS and actually engaging in the first phone smoking cessation counseling session) and *follow through* with treatment (i.e., engaging in the Week 4 counseling session). The two positive (non 0) incentive tiers were selected based on the results of earlier work that used \$30 incentives to improve counseling session attendance, and through this pathway, abstinence rates among low-income smokers. Participants will be paid by mailed check or gift card.

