Analysis. Cost data will come from: healthcare system costs in terms of outreach communications, TCOS time (related to outreach and counseling efforts), implementation costs, incentive costs, and medication expenditures (including related physician screening when it occurs). We will use methods recommended by the US Panel on Cost-Effectiveness in Health and Medicine¹⁰ and consistent with our prior research. We will measure costs from a societal perspective using data on smoking cessation benefits from publicly available Medicare and Medicaid reimbursement rates. Cost estimates will be converted to a common year and QALYs will be computed, using a rate of 3% to discount future outcomes and costs to present value. We will also conduct probabilistic sensitivity analyses to account for uncertainty. We will determine net monetary benefit (NMB), cost per quit (using 6 month abstinence rates), and incremental cost-effectiveness ratios (ICERs)¹¹. The components of NMB will be the added costs of the various incentive levels and the monetized value of the QALYs added by the treatments. Total intervention and implementation costs (including outreach and added TCOS time for intervention, implementation, and incentives) will be compared to program costs of the usual care approach to tobacco use (the TCOS intervention program prior to the incentive study implementation).

- To determine the representativeness of smoking treatment reach and smoking abstinence outcomes generated by the various engagement incentive amounts with regard to different groups of smokers: e.g., those low in socio-economic status, priority populations, different racial and ethnic groups.

Analysis. We will extract data from the EHR to characterize the healthcare system population of patients who smoke with regard to such factors as: gender, race, ethnicity, insurance mix. Such person factors will be related to the likelihood that the patient: responds to TCOS outreach, agrees to accept smoking treatment (agrees to a TQD and completes a counseling call), completes up to 3 counseling calls, picks up smoking medications, and achieves long-term abstinence. Logistic regression will be used to examine the likelihood that different person factors are significantly related to the various outcomes under the different incentive levels.

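### The plan gives no clear route for counting treatment engagement among patients who are randomised but decline the research, and does not say how they enter the primary analysis

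*Combined protocol and SAP*

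**What the plan says.** **Order of events.** Section 6.5 puts randomisation in the contact call and states of the incentive offer: "This offer will occur prior to the patient's provision of consent to participate in research". Randomised decliners must therefore exist.

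**Care for decliners.** When a patient refuses the study, 6.5 has the outreach specialist explain the usual-care options and "provide quit smoking treatment as usual". Section 7.0 adds that counselling and medication "will be identical for both those who chose to participate in the study and those who do not".

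**Endpoint.** Section 4.2 gives "Patient engagement in smoking cessation treatment (defined as setting a TQD and completing the two phone counseling calls". The primary aim in 9.3 and the power statement in 9.4 also describe a TQD plus two calls. None of these names research consent. The only text joining the two ideas is the parenthesis in 6.5: "their treatment engagement (which necessarily includes agreement to it/consent".

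**Data access.** For decliners, 6.4 says: "Only limited patient and systems data will be shared with the research team documenting which patients were called" and declined. Sections 6.4 and 8.2 describe individual data on enrolled participants. Section 6.4 obtains authorisation for EHR data within the consent call, and 10.7 describes EHR data as obtained with consent. Against this, the exploratory representativeness analysis in 9.3 plans an EHR extraction on the whole smoking population and relates person factors to whether a patient "completes up to 3 counseling calls, picks up smoking medications".

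**Analysis set.** The synopsis (2.1) calls the analysis intention-to-treat, and 9.3 takes percentages of those in each condition. Section 4.1 speaks of participants and enrollees. No section says what happens to a patient who was randomised and did not consent.

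**The concern.** A decliner who sets a TQD and completes both calls has done what the endpoint describes, but those calls have no stated path into the primary dataset. Two outcomes are then possible.

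- The decliner stays in the denominator and is scored as not engaged. The trial then measures consenting and engaging together. If declining is commoner in the $0 arm, the control rate falls and the incentive effect is inflated. That pattern is plausible, because declining gives up $50 or $100 in the paid arms and no engagement money in the $0 arm.
- The decliner is dropped. The comparison then conditions on a choice made after randomisation, which the offer itself can influence.

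The primary contrast is at stake, and with it the exploratory cost per additional smoker engaged.

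**Working it through.** **Inputs from 9.4:** control engagement 15%, target 27%, 180 per arm, two-sided alpha .05, power .80. **Not in the documents:** the share of engaged patients in each arm who decline the research. All shares below are assumptions.

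**1. The plan's own figure.** Pooled-variance formula, mean rate 0.21:

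n = [1.960·√(2·0.21·0.79) + 0.842·√(0.15·0.85 + 0.27·0.73)]² / 0.12² = [1.960·0.5760 + 0.842·0.5697]² / 0.0144 = 179.7, so 180 per arm. Power at 180 is 0.801. The stated sample size reproduces.

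**2. Decliners scored as not engaged, no true effect.** Counted rate = true rate × (1 − share missed). With counted difference d, SE0 the pooled and SE1 the unpooled standard error, the two-sided rejection probability is Φ((d − 1.960·SE0)/SE1) + Φ((−d − 1.960·SE0)/SE1). True rate 15% in both arms, 180 per arm, 5% missed in the paid arm (0.15 × 0.95 = 14.25% counted):

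| Missed in $0 | Counted in $0 | Spurious difference | Rejection |
|---|---|---|---|
| 10% | 13.5% | 0.75 points | 5.5% |
| 20% | 12.0% | 2.25 points | 9.7% |
| 30% | 10.5% | 3.75 points | 19.0% |

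For the middle row, SE0 = 0.03559 and SE1 = 0.03557, so the two terms are Φ(−1.329) + Φ(−2.594) = 0.092 + 0.005 = 0.097.

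**3. Decliners scored as not engaged, true 15% v 27%.**

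| Missed in $0 / paid arm | Counted rates | Difference | Power |
|---|---|---|---|
| 0% / 0% | 15.0% v 27.0% | 12.0 points | 0.80 |
| 10% / 0% | 13.5% v 27.0% | 13.5 points | 0.89 |
| 20% / 0% | 12.0% v 27.0% | 15.0 points | 0.95 |
| 30% / 0% | 10.5% v 27.0% | 16.5 points | 0.98 |
| 20% / 20% | 12.0% v 21.6% | 9.6 points | 0.68 |
| 10% / 20% | 13.5% v 21.6% | 8.1 points | 0.52 |

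Excess loss in $0 inflates the effect. Equal loss, or more loss in the paid arm, shrinks it.

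**4. Consenters only, true 15% v 27%.** Rate among consenters = engaged / consented. Suppose all engaged patients consent. With assumed consent of 30% in $0 and 50% in the paid arm, the rates are 0.15/0.30 = 50% and 0.27/0.50 = 54%, a 4-point difference. With 50% consent in both arms they are 0.15/0.50 = 30% and 0.27/0.50 = 54%, a 24-point difference. The result depends on consent behaviour as well as engagement.

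**The case against.** A reader might infer three stronger things, and the documents do not support them.

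- *That the endpoint itself requires research consent.* The definitions in 4.2, 9.3 and 9.4 do not mention it. The parenthesis in 6.5 explains why the offer must come first; its wording about consent is ambiguous, and it is not a scoring rule.
- *That treated decliners are scored as failures.* No section says so. The intention-to-treat label makes it a natural reading, but the enrolment language in 4.1 allows a consenters-only analysis. The population EHR extraction in 9.3 shows that wider data are contemplated, although for an exploratory aim and without resolving the consent-based limits in 6.4, 8.2 and 10.7.
- *That the loss is largest in the $0 arm and the effect is therefore inflated.* Section 6.4 does anticipate that refusal may follow disappointment with the amount. However, the $0 script in Attachment B also mentions possible money, the consent script withholds incentive amounts, and the follow-up payments are open to every arm. The scripted branch for refusing the study gives a phone number and ends the call without setting a TQD, so treated decliners may be few. No figure is given on any of this.

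These points remove any claim to a known direction or size. They leave the gap: identical care is open to randomised decliners, their engagement has no clear path into the primary data, and their place in the analysis is undefined.

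**Conclusion.** The point holds as a gap in ascertainment and in the definition of the analysis set. It is not a demonstrated bias in favour of the incentive. Followed as written, the plan either misses engagement among randomised decliners or drops them after randomisation, and both can distort the primary comparison. Under the assumed shares, the effect on type I error runs from negligible (5.5% at 10% v 5% loss) to serious (19% at 30% v 5%), while equal 20% loss costs power instead (0.68 against the planned 0.80). The calculations assume 180 randomised per arm and, for the error rates, true engagement of 15% in both arms. The sample size of 540 is unaffected. This is a cheap improvement, best made before data collection, because analysis cannot recover fields that were never requested.

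**What to change.** - In 4.2, 6.5 and 9.3, define the primary analysis set as all randomised patients. Take the TQD and completion of the two qualifying calls from GHC-SCW records for all of them, whether or not they consented.
- In 6.4, add three fields to the limited decliner data: assigned arm, TQD set and calls completed. Supply them coded or de-identified, under an IRB-approved waiver or equivalent, and bring 8.2 and 10.7 into line.
- Clarify the parenthesis in 6.5 so that engagement does not depend on research consent.
- Report by arm the numbers who consented and who declined but were treated. Keep consented-and-engaged as a secondary outcome.

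The cost is an IRB and HIPAA amendment, a small addition to an extract already planned, and wording changes. The apparent incentive effect may become smaller once treated decliners are counted.

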7.0 Study Treatments and Experimental Conditions

Smoking cessation treatments will not be experimentally manipulated or varied as a function of research participation. Participants and non-participants will be treated per standard clinical protocols for tobacco use. The experimental conditions (i.e., the incentives) in the study are intended to effect smoker *engagement* in treatment as offered by healthcare system personnel. The primary differences between research study participation and usual care with regard to smoking treatment are: 1) the consent process, 2) randomization to treatment engagement incentive condition and provision of such incentive, 3) follow-up to determine patient smoking status. Importantly, actual smoking cessation treatments (counseling and medications, the existing GHC-SCW standard of care) will be identical for both those who chose to participate in the study and those who do not (Figure 2).

7.1 Incentives In 2 of our recent studies^{4,5}, incentive-driven increases in counseling use mediated incentive effects on abstinence in Medicaid-insured smokers. Given the significant savings associated with smoking cessation⁸, modest incentives to engage in treatment may well be cost-effective if they increase quitting. Modest incentives (\$25 or \$50) also improve attendance at primary care visits⁹. Thus, evidence supports modest, utilization-contingent incentives for use of both smoking cessation and primary care treatment. The proposed project

will evaluate the effects of incentives of varying magnitude for smoking treatment engagement (rather than achieving abstinence) in primary care.

To identify an especially effective incentive amount, three different incentive value conditions will be evaluated (0, \$100, and \$50). The incentive will be tied to readily observable *initiation* of treatment (i.e., setting a target quit date within 30 days on a call with a TCOS and actually engaging in the first phone smoking cessation counseling session) and *follow through* with treatment (i.e., engaging in the Week 4 counseling session). The two positive (non 0) incentive tiers were selected based on the results of earlier work that used \$30 incentives to improve counseling session attendance, and through this pathway, abstinence rates among low-income smokers. Participants will be paid by mailed check or gift card.

8.0 Detailed Study Procedures: Recruitment and Assessments

8.1 Recruitment As noted in the enrollment flow diagram in Attachment A, recruitment will occur over the phone (in the Treatment Planning call) following a patient response to standard TCOS outreach. TCOS as per their current GHC-SCW usual care protocol will provide callers with advice to quit and an overview of cessation treatment options. The TCOS will assess the smoker's readiness to quit in the next 30 days as per usual care. In accordance with randomized condition, the TCOS will offer the appropriate intervention incentive per the Invite Script (Attachment B). For those who tell the TCOS that they are ready to quit within 30 days, the TCOS will offer treatment enrollment and provide standard care per the existing tobacco treatment program of the GHC-SCW healthcare system (e.g., setting quit date, arranging timing of treatment contacts: See Figure 2.).

The TCOS will be trained to present information about the Treatment Engagement Incentive offer, assessing eligibility, informed consent, and research assessment processes in a standardized manner.

UW-CTRI personnel will be responsible for: conducting telephone follow-up interviews 3- and 6-months post-TQD and meeting with patients to verify claimed abstinence 6-months post-TQD via biochemical testing (breath CO, urine, and/or saliva testing without biobanking). The

Figure 2. GHC-SCW Healthcare System Standard Tobacco Treatment Program

All patients on the Cigarette Users Registry receive:

- Quarterly Bulk Outreach via postal mail and MyChart promoting the tobacco treatment program services
- Care Management telephonic outreach calls by TCOS following each primary care visit and no less than once per year.

Patients are offered ongoing access to resources but expected to set a target quit date (TQD) to focus cessation planning and arrange medications. Elements include:

- 3 brief telephone counseling sessions with a Certified Tobacco Treatment Specialist (TCOS)
 - 3-5 days pre-,
 - 5-7 days post- (Week 1),
 - 4 weeks post-TQD (Week 4)
- Smoking cessation pharmacotherapy including combination NRT, varenicline, or any of 7 FDA approved medications.
- Integrated referrals to:
 - primary care physician
 - WI Tobacco Quit Line
 - SmokefreeTXT program
- Weekly facilitated Tobacco Use Support Group
- Ongoing TCOS support through MyChart (EHR patient portal) and phone

biochemical testing visit will be conducted at UW-CTRI or a practical location of the participant's choosing.

Personnel from both the healthcare system and UW-CTRI will therefore have contact with study participants and/or their data. Coordination of all activities will be led by UW-CTRI and UW-CTRI will perform all data analyses. All data transmissions to and from UW-CTRI will occur via secure, HIPAA-compliant means via capture in REDCap or SFTP or secure Box file transfers.

8.2 Assessment Plan

Baseline assessment (See uploaded Baseline Assessment and uploaded List of EHR Data to Be Extracted). At enrollment, TCOS will assess tobacco use history and smoking cessation history, dependence, motivation and self-efficacy related to quitting smoking, attitudes about and beliefs regarding smoking cessation treatments, and education. EHR data regarding age, sex, race, ethnicity, contact information, communication preferences, and documentation regarding social determinants of health (e.g., food insecurity, housing insecurity, financial strain) educational attainment will be obtained. Chronic medical conditions and healthcare utilization over the past year will be extracted from EHR data, as well.

Intra-treatment assessments (See uploaded Intra-Treatment Assessment). At the 3 standard treatment telephone counseling calls, TCOS will assess daily smoking since last contact, counseling engagement, withdrawal, self-efficacy, and use of all nicotine/tobacco products.

Follow-up assessments (See uploaded Follow-up Assessment). UW-CTRI staff will conduct 15-25-minute follow-up interviews 3- and 6-months after study enrollment to assess past 7-day smoking, use of smoking cessation treatments, use of all nicotine/tobacco products, brief demographic characteristics, and treatment satisfaction. Participants will receive \$20 for participating in the 6-month follow-up interview and \$50 for attending the 6-month biochemical confirmation visit at 6 months.

To enhance follow-up interview and visit completion rates, participants will be texted, mailed, sent MyChart messages or sent automated phone calls (depending on their communication preferences as noted in the EHR and during enrollment) to remind them of follow-ups.

Although this program will evaluate interventions delivered by healthcare system personnel (Tobacco Cessation Outreach Specialists), follow-up data collection procedures and collation of data from multiple sources/sites necessary for thorough program evaluation are the responsibility of the UW-CTRI study investigators. To achieve the study aims, UW-CTRI investigators require access to identifiable patient data on all enrolled participants. At UW-CTRI, all study data will be stored in a HIPAA-compliant and secure manner on Department of Medicine servers with UW-CTRI-controlled password access. Staff trained in human subjects research and HIPAA compliance will link these datasets using a random subject identifier and will then de-identify the data for analyses.

